7.2 Participant Discontinuation/Withdrawal from the Study

- A participant may withdraw from the study at any time at his/her own request or may be withdrawn at any time at the discretion of the investigator for safety, behavioural or compliance reasons.
- At the time of discontinuing from the study, an early discontinuation visit should be conducted, as shown in the SoA. See SoA for data to be collected at the time of study discontinuation and follow-up and for any further evaluations that need to be completed.
- The reason for discontinuation will be recorded in the eCRF.
- If the participant withdraws consent for disclosure of future information, the sponsor may retain and continue to use any data collected before such withdrawal of consent.
- If the participant withdraws consent for any further contact, the investigator will explain in the medical records that the participant was also withdrawn from study procedures. This information must be entered in the eCRF.
- If a participant withdraws from the study, he/she may request destruction of any samples taken and not tested, and the investigator must document this in the site study records.
- A participant will be withdrawn from the study if they have inadequate testosterone suppression (defined as >50 ng/dL detected at least 30 days after administration of study intervention and on two consecutive measurements at least 2 weeks apart, at either a scheduled or unscheduled study visit).

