9.3 Analysis Sets

For the purposes of analysis, the following analysis sets are defined:

Participant Analysis Set	Description
Screened	All participants screened (i.e. who signed the informed consent).
Safety Set	The safety set will contain all participants who receive the single dose of study intervention.
Full Analysis Set	The FAS will contain all treated participants who complete the study or is a treatment failure. Completing the study is defined as having serum testosterone measurement at baseline, Day 29 and Day 169. Treatment failure is defined as escaping castration (testosterone level ≥ 50 ng/dL) at any assessments on and after Day 29 during the study, or premature discontinuation from the intervention period due to drug-related reasons (adverse event or death).
Per Protocol Set	All participants in the FAS who have no impacting major protocol deviations (i.e. that could potentially affect the primary efficacy endpoint outcome for the participant) as described in the protocol deviations document.
Rich PK Analysis set (for non-compartmental analysis)	Participants in the PK/PD subset who receive one dose of study intervention, have no major protocol deviations affecting the PK variables, and who have a sufficient number of plasma concentrations to estimate the main PK parameters (maximum observed plasma drug concentration (C_{max}), time to maximum observed drug concentration (t_{max}) and area under the plasma concentration time curve (AUC))
Population PK Analysis Set	All participants who received one dose of triptorelin and who have at least one triptorelin plasma concentration and no major protocol deviations affecting PK variables.

Participant Analysis Set	Description
Rich PD Analysis Set	all participants in the PK/PD subset who have a sufficient number of PD (testosterone) measurements to estimate the main PD parameters (maximum observed concentration (C_{max}), time to maximum observed concentration (t_{max}) and time to castration (t_{castr}))

FAS=full analysis set; PD=pharmacodynamic PK=pharmacokinetic

The efficacy analysis for the primary and secondary efficacy endpoints will be presented for the full analysis set (FAS) and per protocol (PP) population. The analysis of the safety data will be performed based on the safety set and analysis of PK and PD in the relevant PK analysis set

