4 ANALYSIS SETS

Screened Set

The screened set will contain all participants screened (i.e. who signed the informed consent).

Full Analysis Set (FAS)

The FAS will contain all treated participants who complete the study or is a treatment failure. Completing the study is defined as having serum testosterone measurement at baseline, Day 29 and Day 169. Treatment failure is defined as escaping castration (testosterone level ≥ 50 ng/dL or 1.735 nmol/L) at any assessments on and after Day 29 during the study, or premature discontinuation from the intervention period due to drug-related reasons (adverse event or death).

Per Protocol Set (PPS)

The PPS will contain all participants in the FAS who have no impacting major protocol deviations (i.e. that could potentially affect the primary efficacy endpoint outcome for the participant) as described in the protocol deviations document.

Safety Set

The safety set will contain all participants who receive the single dose of study intervention.

Rich PK Analysis Set (for non-compartmental analysis)

The rich PK analysis set will contain all participants in the PK/PD subset who receive one dose of study intervention, have no major protocol deviations affecting the PK variables, and who have a sufficient number of plasma concentrations to estimate the main PK parameters (maximum observed plasma drug concentration (C_{max}), time to maximum observed drug concentration (t_{max}) and area under the plasma concentration time curve (AUC)).

The criteria of major protocol deviations affecting the PK variables will be defined in the protocol deviation document. The process to review major protocol deviations potential impact on PK parameters will be ongoing and the final Rich PK Analysis Set will be determined during data review meeting.

Population PK Analysis Set

The population PK analysis set will contain all participants who received one dose of triptorelin and who have at least one triptorelin plasma concentration and no major protocol deviations affecting PK variables.

Rich PD Analysis Set

The rich PD analysis set will contain all participants in the PK/PD subset who have a sufficient number of PD (testosterone) measurements to estimate the main PD parameters (maximum observed concentration (C_{max}), time to maximum observed concentration (t_{max}) and time to castration (t_{castr})).

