5.7.1.3 Statistical/analytical issues

Adjustments for Covariates

This is a single-arm study, and no statistical comparisons will be performed, so covariates adjustment is not required.

Interim Analyses and Data Monitoring

Please refer to section 3.

Multicentre Studies

This is a multicentre study conducted in China.

Multiple Comparisons/Multiplicity

No multiple testing will be performed in this study because this is a single-arm descriptive safety and efficacy study.

Active-Control Studies Intended to Show Equivalence (if applicable)

Not applicable.

5.7.2 *Analysis of Primary Efficacy Endpoint*

5.7.2.1 *Endpoint, Treatment Effect and Estimand Definition*

The co-primary endpoints of efficacy are

- To determine the percentage of participants achieving castrate levels of serum testosterone (<50 ng/dL or 1.735 nmol/L) on Day 29 ± 3 days (Week 4) and
- To determine the percentage of participants maintaining the castrate levels of serum testosterone (<50 ng/dL or 1.735 nmol/L) from Week 8 (Day 57 ± 3 days) to Week 24 (Day 169 ± 3 days).

Percentage of participants achieving castrate levels of serum testosterone on Day 29

The percentage of participants achieving castrate levels of serum testosterone on Day 29 will be obtained as the number of participants achieving castrate levels on Day 29, divided by the number of participants in the FAS. The formula is

$$\text{Percentage} = \frac{\text{Number of participants achieving castrate levels on Day 29}}{\text{Number of participants in the analysis set}} \times 100$$

Percentage of participants maintaining castrate levels from Week 8 to Week 24

Percentage of participants maintaining castrate levels of serum testosterone from Week 8 to Week 24 for the FAS will be calculated as the number of participants achieving castrate levels of serum testosterone at all visits from Week 8 to Week 24, divided by the number of assessable participants in the analysis set. The formula is

$$\text{Percentage} = \frac{\text{Number of participants maintaining castrate levels from Week 8 to Week 24}}{\text{Number of assessable participants in the analysis set}} \times 100$$

To derive the percentage of participants maintaining castration levels of testosterone, missing data between Week 8 and Week 24 will be handled as follows:

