- (a) In participants escaping castration at a certain visit (The escape event is defined as participant with a testosterone level >50 ng/dL), subsequent missing data is irrelevant; that is to say, participant will be treated as failure in that case.
- (b) Participants maintaining castration up to a certain visit with missing data afterwards (drop-out due to non-drug-related reasons) will be excluded from the analysis.
- (c) Participants maintaining castration up to a certain visit with missing data afterwards (drop-out due to drug-related reason) will be treated as having escaped castration (failure). Drug-related reason for drop-out is drug-related adverse event or death.
- (d) Missing data at 1 or more visit(s) between two visits where castration levels are maintained will be handled as missing for that particular visit, and the participant will be considered to have maintained castration if all visits with available results are maintained.

To derive the percentage of participants maintaining castrate levels of testosterone, assessable participants are defined as the number of participants having values at all visits and all participants having missing data according to the criteria a), c) and d) mentioned above. Participants having missing data according to the criteria b) will be excluded from this calculation. Participants who discontinue before Week 8 will also be excluded from this calculation.

Because this is a descriptive post-approval commitment study, and the protocol was approved before National Medical Products Administration (NMPA) implementation of ICH E9 (R1), estimands will not be considered for this study.

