5.7.2.3 Sensitivity Analysis

In addition, to further validate the analysis results of the primary endpoint, below sensitivity analyses will be conducted.

Sensitivity analysis 1: Analysis defined in section [5.7.2.2](#) (primary analyses for co-primary endpoints) will be repeated on the PPS.

Sensitivity analysis 2: Survival analysis to estimate the percentage of participants maintaining castrate levels from Week 8 to Week 24

Percentage of participants with castration levels (<50 ng/dL or 1.735 nmol/L) from Week 8 to Week 24, treated as a time-to-event endpoint, will be analysed by Kaplan-Meier method.

The event is defined as occurring in participants with a testosterone level \geq 50 ng/dL or 1.735 nmol/L between Week 8 and Week 24 (escape event), and it will be presented as number of participants with escape event (event number), percentage of participants with escape event, achievement (<50 ng/dL or 1.735 nmol/L) rate by Week 8, Week 12, Week 16, Week 20, and Week 24 along with 95% CIs (calculated using the Greenwood's formula), minimum, maximum, median and 95% CI for median (calculated using Brookmeyer-Crowley method).

To accommodate drop-out and missing values the following censoring rules will be observed:

Table 5.1 Data Censoring Rules

Subject Discontinued	Week 8 - Week 24/Day of Discontinuation		To Be Handled As
	≥ 1 Missing Testosterone Value	Any Escape*	
Yes	No	No	Censored on day of last measurement
Yes	No	Yes	Event on day of first escape
Yes	Yes	No	Censored on day of last measurement before the first missing
Yes	Yes	Yes	Event on day of first escape
No	No	No	Censored on day of last measurement (date of EOS or Day 169)
No	No	Yes	Event on day of first escape
No	Yes	No	Censored on day of last measurement before the first missing
No	Yes	Yes	Event on day of first escape
No achievement by Week 8			Event on day of Week 8

*The escape (event) is defined as participant with castrate levels of serum testosterone ≥ 50 ng/dL or 1.735 nmol/L.

Below 3 percentages based on different populations are considered for calculation of percentage of participants maintaining castrate levels from Week 8 to Week 24:

Sensitivity analysis 3: All participants treated who complete the study or premature discontinuation from the intervention period due to any reasons will be included.

Sensitivity analysis 4: Participants in the FAS or PPS who do not discontinue from the treatment period prematurely due to drug-related reasons will be included.

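### SAP 5.7.2.1 rule (a) defines escape as above 50 ng/dL instead of at or above 50, so a man at exactly 50 with data missing afterwards fits no missing-data rule and can leave the maintenance denominator

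*SAP*

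**What the plan says.** Four current passages bear on the analysis.

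- **Success.** SAP 5.7.2.1 describes the second co-primary endpoint as "maintaining the castrate levels of serum testosterone (<50 ng/dL or 1.735 nmol/L) from Week 8" to Week 24. Its numerator is "the number of participants achieving castrate levels of serum testosterone at all visits from Week 8 to Week 24".
- **Escape in the missing-data rules.** The same section lists rules (a) to (d) for data missing between Week 8 and Week 24. Rule (a) makes later missing data irrelevant once a man has escaped, and treats him as a failure. It adds: "The escape event is defined as participant with a testosterone level >50 ng/dL".
- **Escape in the analysis set.** SAP section 4 admits treatment failures to the FAS, and failure includes "escaping castration (testosterone level ≥ 50 ng/dL or 1.735 nmol/L) at any assessments on and after Day 29". Protocol 9.3 agrees: "escaping castration (testosterone level ≥ 50 ng/dL) at any assessments on and after Day 29 during the study".
- **Escape in the Kaplan-Meier analysis.** SAP 5.7.2.3, sensitivity analysis 2, sets the event at 50 ng/dL or above in its text. The footnote to Table 5.1 repeats this: "The escape (event) is defined as participant with castrate levels of serum testosterone" at or above 50 ng/dL or 1.735 nmol/L.

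Protocol 9.4.2 has the same rule (a) without a threshold. The strict inequality therefore appears only in the SAP, and SAP 2.6 does not list it as a change from the protocol.

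**The concern.** Within one SAP, escape has two thresholds. Where castrate means below 50, its complement is 50 or above, and rule (a) leaves the value 50 in neither class. The missing-data rules decide who enters the denominator of a co-primary percentage, so a value they do not classify can remove a man from the estimate.

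The direction matters. The man at risk of removal is one whom the FAS definition calls a treatment failure, so losing him raises the maintenance rate. If the conflict surfaces only during programming or after database lock, the choice of sign would be made by people who can see whom it affects.

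**Working it through.** **1. The plan's own figures.** Inputs from SAP 2.3: n = 165, null proportion 85%, true proportions 93% and 97.5%, two-sided 0.05, dropout 15%. The critical count r is the smallest with P(X ≥ r | 165, 0.85) ≤ 0.025.

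- P(X ≥ 149) = 0.0309 and P(X ≥ 150) = 0.0173, so r = 150.
- Power at 93%: P(X ≥ 150 | 165, 0.93) = 0.883, as stated (88.3%).
- Power at 97.5%: above 0.9999, as stated (>99.9%).
- Enrolment: 165/0.85 = 194.1, rounded up to 195, as stated.

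None of these depends on the sign in rule (a).

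**2. A man with complete data and one value of 50.** He has values at all visits, so he is assessable. He is not below 50 at all visits, so he is not in the numerator. He counts as not maintained under either sign, and the Kaplan-Meier analysis also counts him as an event. There is no conflict.

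**3. A man with a value of 50, none above 50, who then drops out.**

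| Rule | Condition | Does it apply? |
|---|---|---|
| (a) | value above 50, later data missing | No: 50 is not above 50 |
| (b) | castration maintained, then non-drug-related drop-out | No: 50 is not castrate |
| (c) | castration maintained, then drug-related drop-out | No: 50 is not castrate |
| (d) | missing between two castrate visits | No: no later visit |

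Assessable men are those with values at all visits, plus those with missing data under (a), (c) or (d). He belongs to neither group and so falls out of the denominator. Yet SAP section 4 puts him in the FAS as a treatment failure, and Table 5.1 gives him an event on the day of first escape.

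If he misses a visit and returns, the result depends on how (d) is read. Even then, (d) treats a man as maintained only if all his available results are castrate, so he could not count as a success.

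**4. Size.** Let x men maintain out of n, with one of the n − x failures being this man. Excluding him instead of failing him changes the estimate by

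x/(n − 1) − x/n = x / [n(n − 1)].

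The counts below are illustrative. They take the planned 165 as the denominator. Limits are two-sided 95% Clopper-Pearson, as planned in SAP 5.7.2.2.

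| Case | Counted as failure | Excluded | Shift in estimate |
|---|---|---|---|
| Near the planned 93% | 153/165 = 92.7% (87.6 to 96.2) | 153/164 = 93.3% (88.3 to 96.6) | 153/(165 × 164) = 0.57 points |
| Near the sizing boundary | 149/165 = 90.3% (84.7 to 94.4) | 149/164 = 90.9% (85.4 to 94.8) | 149/(165 × 164) = 0.55 points |

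**5. Range over the number of such men, k.** The documents do not give k, so it is an assumption. With x = 153 and n = 165, the shift is 153k / [165(165 − k)]:

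- k = 0: none
- k = 1: 0.57 points
- k = 2: 306/26,895 = 1.14 points
- k = 3: 459/26,730 = 1.72 points

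**The case against.** The strongest reply is that rule (a) is a missing-data rule and not the endpoint definition. The endpoint is fixed by the numerator, which needs a value below 50 at every visit, and the FAS definition already labels a man at 50 a failure. That stands, and it limits the point to a value of exactly 50 with data missing afterwards. It does not close the gap, because rules (a) to (d) also determine the denominator.

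Four stronger readings are tempting, and the documents do not support them.

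- **That the primary and Kaplan-Meier analyses count different failures in general.** They agree on a value of 50 in any man with complete data.
- **That a man at 50 could count as maintained, giving 150/165 against 149/165.** The numerator never admits a value of 50. The open question is excluded against failed.
- **That one man could decide the trial at 85%.** The second row of the size table does straddle 85%, but only at that chosen count; at the planned rate both lower limits are well above it. The 85% appears only in the sizing text. Protocol 9.1 plans no hypotheses, and Protocol 9.4.1.2 and SAP 5.7.1.1 plan no formal testing.
- **That Protocol 7.2 shows the same error.** Its withdrawal criterion, "defined as >50 ng/dL detected at least 30 days after administration of study intervention", also requires two consecutive measurements at least 2 weeks apart. It is a rule for managing participants and need not share the inequality of a single-value analysis event. It is outside this point, and no view is taken on it.

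**Conclusion.** Rule (a) is wrong as written. It contradicts the FAS definition in both documents and the Kaplan-Meier event definition, and it is not the complement of castrate. The practical effect is small: about 0.6 percentage points for each man with a value of exactly 50, none above 50, and missing data afterwards, in favour of the product if he is excluded.

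This rests on a literal reading of rules (a) to (d), and on a denominator near the planned 165. The number of such men may well be zero. Protocol 8.2.1 names the assay method but gives no reporting precision, so the documents do not allow an estimate of how often a result of exactly 50 will occur. The point does not put the sample size, the power or the endpoint's definition of success in doubt.

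**What to change.** In SAP 5.7.2.1 rule (a), define the escape event as testosterone at or above 50 ng/dL (1.735 nmol/L). This is the complement of castrate and matches SAP section 4, Protocol 9.3 and SAP 5.7.2.3. A man at exactly 50 with data missing afterwards then falls under rule (a), stays in the denominator and counts as a failure.

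The cost is one sign and one added unit in the SAP, made before database lock. It needs no new data, no resizing and no new judgement, because every other analysis definition of escape already uses this threshold. Protocol 9.4.2 needs no change, as its rule (a) gives no threshold.

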9.4.1.3 Statistical/Analytical Methods

Statistical analyses will be performed by an external CRO, managed by the sponsor's Biometry department.

Demographic and Other Baseline Characteristics

Descriptive summary statistics (n, mean, standard deviation (SD), median, minimum, maximum) or frequency counts of demographic and baseline data (medical history, concomitant disease (predosing AEs and ongoing medical history, prior medications and therapies, etc.) will be presented for the FAS, PP and safety sets.

Participant Disposition and Withdrawals

The numbers and percentages of participants screened and included in each of the populations will be tabulated overall and by centre. The reasons for participant exclusions from each of the populations will also be tabulated. Primary reasons for discontinuation of study will be tabulated.

Adjustment for Country/Centre Effects

Descriptive analysis will be carried out to evaluate any possible centre effect.

9.4.2 *Analysis of Primary Endpoints*

The co-primary efficacy variables are

- percentage of participants achieving castrate levels of serum testosterone (<50 ng/dL or 1.735 nmol/L) and
- percentage of participants maintaining the castrate levels from Week 8 to Week 24.

The percentage of participants achieving castrate levels of serum testosterone (<50 ng/dL or 1.735 nmol/L) on Day 29 will be obtained as the number of participants with castrate levels at the visit, divided by the total number of participants on Day 29 in the considered population.

Percentage of participants maintaining the castrate levels of serum testosterone (<50 ng/dL or 1.735 nmol/L) from Week 8 to Week 24 will be calculated as the number of participants with castrate levels at all visits from Week 8 to Week 24, divided by the total number of assessable participants.

To derive the percentage of participants maintaining castration levels of testosterone, missing data will be handled as follows:

- (a) In participants escaping castration at a certain visit, subsequent missing data is irrelevant.
- (b) Participants maintaining castration up to a certain visit with missing data afterwards (drop-out due to non-drug-related reasons) will be excluded from the analysis.
- (c) Participants maintaining castration up to a certain visit with missing data afterwards (drop-out due to drug-related reasons) will be treated as having escaped castration (failure).

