- (d) Missing data between two visits where castration levels are maintained will be handled as missing for that particular visit, and the participant will be considered to have maintained castration.

To derive the percentage of participants maintaining castrate levels of testosterone, assessable participants are defined as the total number of all participants having values at all visits and all participants having missing data according to the criteria a), c) and d) mentioned previously. Participants having missing data according to the criteria b) will be excluded from this calculation.

Co-primary endpoints will be tabulated with two-sided 95% (95% CI) using the Clopper-Pearson exact method.

9.4.3 *Analysis of Secondary Endpoints*

9.4.3.1 *Prostate-Specific Antigen*

The secondary efficacy variable is the percent change in PSA from baseline (prior to injection) measured at Week 12 and Week 24. Percent change in PSA is defined as the absolute value of difference between the PSA values at Week 12 and Week 24 and the baseline value divided by the baseline value.

PSA percent change from pre-treatment Day 1 will be reported at each subsequent visit, using descriptive statistics.

9.4.3.2 *Pharmacokinetic and Pharmacodynamic Data Analysis*

Description of Triptorelin and Testosterone Concentrations

Individual plasma or serum concentrations of triptorelin and testosterone will be listed and summarised by visit and time points using descriptive statistics for continuous variables (number of available observations, mean, median, SD, minimum, maximum, geometric mean, and geometric coefficient of variation (assuming log normally distributed data). Data will be

summarised for the PK/PD subset and overall. Individual and mean triptorelin and testosterone concentration time profiles, as well as spaghetti plots, will be generated.

Non-compartmental Analysis

The PK analysis of triptorelin plasma concentrations and testosterone serum concentrations of the rich sampling PK/PD subset will be performed by the non-compartmental analysis (NCA) approach using Phoenix WinNonlin PK program version 8.3 or higher. The following PK parameters will be calculated if warranted by the data:

- maximum observed concentration (C_{\max})
- time to maximum observed blood concentration (t_{\max})
- (for triptorelin only) area under the plasma concentration time curve from time 0 to the time of the last quantifiable concentration (AUC_{last})

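### SAP 5.7.2.1 drops everyone who leaves before Week 8 from the maintenance co-primary, although protocol 9.4.2 scores drug-related drop-outs castrate at Day 29 as failures; SAP 2.6 does not declare the change

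*SAP*

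**What the plan says.** Protocol 9.4.2 defines maintenance as castrate testosterone at every visit from Week 8 to Week 24, among assessable participants, and gives four missing-data rules. Rule (a): "In participants escaping castration at a certain visit, subsequent missing data is irrelevant". Rule (b) removes participants who were castrate up to some visit and then dropped out for non-drug-related reasons. Rule (c) covers the same pattern when the reason is drug-related: "drop-out due to drug-related reasons) will be treated as having escaped castration (failure". Rule (d) tolerates gaps between castrate visits. The denominator is everyone with complete values plus those under (a), (c) and (d). The one stated exclusion is: "Participants having missing data according to the criteria b) will be excluded from this calculation". None of the rules names a first visit.

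SAP 5.7.2.1 repeats the four rules with two changes. Its lead-in confines them to data missing between Week 8 and Week 24, and after the definition of assessable participants it adds: "Participants who discontinue before Week 8 will also be excluded from this calculation". It also narrows the meaning of drug-related: "Drug-related reason for drop-out is drug-related adverse event or death".

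Both documents define the FAS in the same way (protocol 9.3, SAP 4). It holds completers, who need testosterone values at baseline, Day 29 and Day 169, and treatment failures. A treatment failure is a participant "escaping castration (testosterone level ≥ 50 ng/dL) at any assessments on and after Day 29 during the study", or one who discontinued for a drug-related reason. SAP 2.6, the table of changes from the protocol, has one row, on the analysis set for medical history and medications.

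**The concern.** The SAP changes the denominator of a co-primary endpoint without saying so, and the change is not neutral. A participant who leaves before Week 8 has no Day 169 value, so he can be in the FAS only as a treatment failure, and he can never be a maintainer. Excluding him removes a non-maintainer from the denominator and nothing from the numerator. In a single-arm study without a comparator, the reported percentage and its interval are the result.

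The clearest case is a participant who is castrate at Day 29 and is then lost before Week 8 to a drug-related adverse event or death. That is the outcome rule (c) was written to count as failure.

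**Working it through.** **1. The plan's own figure.** Inputs from protocol 9.2 and SAP 2.3: n = 165, null 85%, alternative 93%, two-sided 5%, 15% dropout. The smallest r with P(X ≥ r | 165, 0.85) ≤ 0.025 is r = 150 (attained 0.0173). P(X ≥ 150 | 165, 0.93) = 0.8832, which matches the stated 88.3%. 165/(1 − 0.15) = 194.1, rounded up to 195. So 165 is a fair base for illustration.

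**2. The texts side by side, for participants who leave before Week 8.**

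| Participant | Protocol 9.4.2 | SAP 5.7.2.1 |
|---|---|---|
| Castrate at Day 29, drug-related drop-out | Failure, rule (c) | Excluded |
| Value ≥50 ng/dL on or after Day 29, then leaves | Failure under rule (a), on one reading | Excluded |
| Drug-related drop-out before Day 29 | Generally not reached by (a), (c) or (d) | Excluded |
| Non-drug-related drop-out, no value ≥50 ng/dL on or after Day 29 | Excluded if castrate before leaving, rule (b); not in the FAS | Excluded; not in the FAS |

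The first row is a direct contradiction. The second depends on interpretation. In the third, entry requires more than 150 ng/dL, and outside the PK/PD subset the first post-dose testosterone sample is Day 29. Castration has therefore generally not been shown, and the two texts do not clearly differ.

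**3. Direction.** Let x be the maintainers, n the FAS denominator with early failures kept, and k the early failures removed. Then x/(n − k) > x/n for any k > 0 and x > 0.

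This assumes that an early-withdrawal sample is not read as the Day 169 value. The assumption needs stating, because SAP 5.1.1.3 gives end of study and early withdrawal a single visit label and SAP 6.2 says no remapping is done.

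**4. Size.** Take x = 153 (0.93 × 165 = 153.45). The Clopper-Pearson lower limit is the 2.5% quantile of a beta distribution with parameters x and n − k − x + 1.

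| k removed | Rate | Lower 95% limit |
|---|---|---|
| 0 | 153/165 = 92.73% | 87.64% |
| 1 | 153/164 = 93.29% | 88.32% |
| 2 | 153/163 = 93.87% | 89.01% |
| 3 | 153/162 = 94.44% | 89.72% |
| 4 | 153/161 = 95.03% | 90.44% |

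The first case adds 93.29 − 92.73 = 0.56 points to the rate and 88.32 − 87.64 = 0.68 to the lower limit.

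The range of k is an assumption. The planned 97.5% Day 29 rate implies 0.025 × 165 = 4.1 participants not castrate at Day 29. That gives a scale for the second row of the step 2 table only, and reaching it would need all of them to leave before Week 8. No figure is given for early drug-related drop-out.

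**5. Timing of withdrawal for non-suppression.** Protocol 7.2 requires a value above 50 ng/dL at least 30 days after dosing, so from Day 31, and a second at least 14 days later, so from Day 45. The Week 8 window opens on Day 57 − 3 = Day 54. The Day 29 window closes on Day 32, so at most one of the two values can come from a scheduled visit before Week 8.

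**The case against.** The strongest reply is that the endpoint starts at Week 8, so a participant who never reached Week 8 is outside it, and that the protocol expects the SAP to be more technical. This is a tenable definition of the endpoint. It is not the one in protocol 9.4.2, which lists who is assessable, includes rule (c) without a starting visit and excludes only rule (b). If the sponsor wants the Week 8 definition, it is a departure to declare.

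A reader might infer more: that the SAP removes participants withdrawn for lack of efficacy whom the protocol plainly keeps as failures. Protocol 7.2 does say "A participant will be withdrawn from the study if they have inadequate testosterone suppression", and it counts values "on two consecutive measurements at least 2 weeks apart, at either a scheduled or unscheduled study visit". The documents do not support the inference in that strength, for three reasons.

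- Applying rule (a) to a value before Week 8 is a reading. It draws on the Day 29 wording in the FAS definition, which governs membership and not maintenance scoring. A participant at or above 50 ng/dL on Day 29 who stays and is castrate at every visit from Week 8 to Week 24 still counts as a maintainer.
- Withdrawal for non-suppression before Day 54 always needs at least one unscheduled sample. Protocol section 8 provides for unscheduled samples for safety or technical reasons, and no efficacy retest is scheduled before Week 8.
- Counting drug-related leavers before Day 29 as failures would be a new rule, not a return to the protocol.

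It can also be said that the sensitivity analyses cover the gap. They do so only in part. Analysis 2 scores non-achievement by Week 8 as an event, but it censors the participant who was castrate at Day 29 and then left. Analysis 3 brings in all discontinuations. Its natural result is conservative, because early leavers cannot enter the numerator, but the SAP does not state how they are scored. Analyses 4 and 5 restrict the population further.

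**Conclusion.** The point holds for drug-related drop-outs who are castrate at Day 29. The protocol scores them as failures, the SAP excludes them, and SAP 2.6 is silent. For participants with a value of 50 ng/dL or more on or after Day 29 who leave before Week 8, the SAP excludes them and the protocol is open to two readings, so their scoring needs to be stated.

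In the FAS the exclusion acts upward only, by about 0.6 points on the rate and 0.7 on the lower limit for the first case at 153/165. This rests on the early-withdrawal sample not standing in for Day 169. The number of cases is not given and may be zero, so the effect is probably small.

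A reader might also infer that the exclusion could decide whether the study succeeds against 85%. The arithmetic can be made to show a crossing: 149/165 has a lower limit of 84.7%, and 149/164 has 85.4%. But the 85% is only the planning null. Both documents state that there are no hypotheses and no formal testing, so what is affected is the reported estimate and interval.

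**What to change.** - In SAP 5.7.2.1, limit the added sentence to participants who discontinue before Week 8 for non-drug-related reasons, so that drug-related drop-outs castrate at Day 29 count as failures under rule (c). Change the lead-in to cover missing data up to Week 24.
- State how participants with a value of 50 ng/dL or more on or after Day 29 who leave before Week 8 are scored. Report the rate with them counted as failures, at least as a sensitivity analysis.
- State in sensitivity analysis 3 that discontinuers without Week 8 to Week 24 values count as non-maintainers.
- State that an early-withdrawal sample does not serve as the Day 169 value.
- If drug-related drop-outs before Day 29 are also to count as failures, list that in SAP 2.6 as a departure from protocol 9.4.2.
- If the sponsor prefers to keep the Week 8 restriction, list it in SAP 2.6 and report the failure-counting version as a named sensitivity analysis.

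The cost is a few sentences and at most a row or two in SAP 2.6. No new data are needed, because testosterone values and reasons for withdrawal are already collected. The downside is that the reported maintenance rate may be slightly lower.
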